7.3 Secondary Efficacy Analyses

Considering the explorative nature of the secondary endpoints, all the inferential results obtained on them will be descriptively interpreted.

7.3.1 Change from Baseline in number of inflammatory lesions (papules and pustules) at end of study (Day 60)

The change from baseline to V4 will be analyzed by means of an Analysis of Covariance (ANCOVA) Model (one model for each comparison to placebo), with change from Baseline to Day 60 in inflammatory lesions as dependent variable, treatment group and L-BT status at screening as explicative factors and baseline count of inflammatory lesions as covariate.

The adjusted mean differences with the corresponding 95% confidence interval will be estimated from the model. The 95% confidence interval for the difference between adjusted mean differences of each active treatment arm versus the placebo arm will be also presented.

7.3.2 Percent of participants showing treatment success (i.e. IGA score of 0 or 1) at end of treatment (Day 30) and end of study (Day 60).

The percent of participants showing treatment success (IGA score of 0 or 1) at the end of treatment (Day 30) and end of study (Day 60) will be separately analyzed by means of a two-sided Cochran Mantel-Haenszel Chi-square test stratified by L-BT status at screening. The Breslow-Day test with Tarone's adjustment for stratified tables will be applied. A two-sided 95% CI for difference of success rate between the treatment groups (each treatment arm vs placebo) will also be computed.

7.3.3 Percent of participants with IGA score of 0 (clear) at end of treatment (Day 30) and end of study (Day 60)

The percent of participants with an IGA score of 0 at the end of treatment (Day 30) and end of study (Day 60) will be separately analyzed by means of a two-sided Cochran Mantel-Haenszel Chi-square test stratified by L-BT status at screening. The Breslow-Day test for stratified tables will be applied. A two-sided 95% CI for difference of success rate between the treatment groups (each treatment arm vs placebo) will also be computed.

7.3.4 Change from Baseline in additional rosacea features at end of treatment (Day 30) and end of study (Day 60)

The following rosacea features will be analyzed:

- 1. Pain, burning/stinging and itching (measured using a 0-10 cm Visual Analogue Scale (VAS))
- 2. telangiectasia (absent=0, mild=1, moderate=2, severe=3)
- 3. ocular manifestations (absent=0, mild=1, moderate=2, severe=3)
- 4. phymatous changes (absent=0, mild=1, moderate=2, severe=3)

For each of the above features, the change from baseline value to the end of treatment (Day 30) and end of study (Day 60) will be separately analyzed by means of an Analysis of Covariance (ANCOVA) (one model for each comparison to placebo) Model, with change from baseline value as dependent variable, treatment group and L-BT status at screening as explicative factors and baseline value as covariate.

The adjusted mean differences with the corresponding 95% confidence interval will be estimated from the model. The 95% confidence interval for the difference between adjusted mean differences of each active treatment arm versus the placebo arm will be also presented.

7.3.5 Change from Baseline in facial non-transient erythema at end of treatment (Day 30) and end of study (Day 60)

The change from baseline to the end of treatment (Day 30) and end of study (Day 60) will be separately analyzed by means of an Analysis of Covariance (ANCOVA) Model (one model for each comparison to placebo), with change from baseline in facial non-transient erythema as dependent variable, treatment group and L-BT status at screening as explicative factors and baseline facial non-transient erythema as covariate.

The adjusted mean differences with the corresponding 95% confidence interval will be estimated from the model. The 95% confidence interval for the difference between adjusted mean differences of each active treatment arm versus the placebo arm will be also presented.

7.3.6 Change from Baseline in Irritable Bowel Syndrome - Symptom Severity Scale Parameters

The following Irritable Bowel Syndrome - Symptom Severity Scale parameter will be analyzed:

- 1. abdominal pain score
- 2. abdominal distention score
- 3. bowel habit satisfaction score
- 4. global severity of abdominal symptoms score

For each of the above features, the change from baseline to the end of treatment (Day 30) and end of study (Day 60) will be separately analyzed by means of an Analysis of Covariance (ANCOVA) Model (one model for each comparison to placebo), with change from baseline value as dependent variable, treatment group and L-BT status at screening as explicative factors and baseline value as covariate.

The adjusted mean differences with the corresponding 95% confidence interval will be estimated from the model. The 95% confidence interval for the difference between adjusted mean differences of each active treatment arm versus the placebo arm will be also presented.

7.3.7 Percent of participants showing treatment success according to Modified IGA Scale The following Modified IGA scales will be used:

Modified IGA scale including erythema but excluding rosacea inflammatory lesions

Modified IGA scale including erythema and rosacea inflammatory lesions

The percent of participants with a Modified IGA score of 0 or 1 (according to the previous definitions) at the end of treatment (Day 30) and end of study (Day 60) will be separately analyzed by means of a two-sided Cochran Mantel-Haenszel Chi-square test stratified by L-BT status at screening. The Breslow-Day test with Tarone's adjustment for stratified tables will be applied. A two-sided 95% CI for difference of success rate between the treatment groups (each treatment arm vs placebo) will also be computed.

7.4 Other Efficacy Analyses

Other efficacy parameters will be summarized descriptively only. These parameters will be collected via a diary and reviewed throughout the course of the study through an electronic Patient Reported Outcome (ePRO) from the randomization visit until the end of the follow up period (30 days after last dose).

7.4.1 Irritable Bowel Syndrome - Symptom Severity Scale

The Irritable Bowel Syndrome - Symptom Severity Scale (IBS-SSS), that has to be collected every ten days, will be summarized descriptively by Study Day for the FAS population. A by-patient listing will be provided.

7.4.2 Dermatology Quality of Life Index

The Dermatology Quality of Life Index (DQLI) consists of 10 questions concerning symptoms and feelings, daily activities, leisure, work, and school, personal relationships, and treatment.

Each question is scored on a four-point Likert scale:

- Very much = 3
- A lot = 2
- A little = 1
- Not at all = 0
- Not relevant = 0
- Question unanswered = 0

The DLQI, that has to be collected every ten days, is calculated by adding the score of each question, resulting in a maximum of 30 and a minimum of 0. The higher the score, the more quality of life is impaired.

The meaning of the DLQI total score is summarized below:

- 0-1 no effect at all on patient's life
- 2-5 small effect on patient's life
- 6-10 moderate effect on patient's life
- 11-20 very large effect on patient's life
- 21-30 extremely large effect on patient's life

The score will be summarized descriptively by Study Day for the FAS population. A by-patient listing will be provided. In addition, the following summary scores will be calculated, listed and summarized descriptively:

- Symptoms and Feelings: sum of questions 1 and 2 (maximum score: 6)
- Daily Activities: sum of questions 3 and 4 (maximum score: 6)

- Leisure: sum of questions 5 and 6 (maximum score: 6)
- Work and School: question 7 (maximum score: 3)
- Personal Relationships: sum of questions 8 and 9 (maximum score: 6)
- Treatment: question 10 (maximum score: 3)

If one question is unanswered, this is allocated a score of 0 and the DLQI score summed in the usual way. If two or more questions are unanswered, the questionnaire is not scored.

When using sub-scales, if the answer to one question in a sub-scale is missing, that sub-scale should not be scored

Scoring of question 7

The first part of question 7 asks: 'Over the last week, has your skin prevented you from working or studying?'

If working or studying are not relevant to the subject, the response is 'Not relevant' (scored 0).

If the skin disease has prevented the subject from working or studying, the answer is 'Yes'. As 'prevention' is the biggest possible impact it is scored the maximum, 3.

If the skin disease has not prevented the subject from working or studying, the answer is 'No'. The subject is therefore asked the following question 'over the last week how much has your skin been a problem at work or studying?'. There are three possible responses to the question 'How much has your skin been a problem at work or studying': 'A lot' (scored 2), 'A little' (scored 1) or 'Not at all' (scored 0).

8 Safety Analyses

All safety measures will be descriptively summarized by treatment group in the SAF population.

8.1 Adverse Events

Adverse events will be presented for the Safety Analysis Set (SAF), by treatment group.

All adverse events will be assigned to a Preferred Term (PT) and will be classified by Primary SOC according to the latest MedDRA version.

Any adverse event which started at or after the first administration of study treatment will be considered as Treatment Emergent Adverse Event (TEAE). If the start date is missing for an AE, the AE will be considered to be treatment emergent. See Section 5.9 for details on partially missing AE start dates.

Adverse events will be reported on a per-patient basis. This means that even if a patient reported the same event repeatedly, the event will be counted only once. Also, the number of events will be presented.

TEAEs relationship to study medications and TEAE severity will be investigated with frequency tables.

In case of missing relationship/severity, the AE is considered related/severe, respectively.

The following tables will be presented:

- Overview of TEAEs showing the number of TEAEs, the number of TESAEs and the number of
 patients with any TEAEs, treatment-related TEAEs, serious TEAEs, treatment-related serious
 TEAEs, severe TEAEs, TEAEs leading to treatment discontinuation and TESAEs with Outcome
 equal to Death;
- 2. Summary of TEAEs by Primary SOC and PT;
- Summary of Related TEAEs by Primary SOC and PT;

- 4. Summary of TEAEs by Primary SOC, PT and maximum Severity;
- 5. Summary of Serious TEAEs by Primary SOC and PT;
- 6. Summary of Related and Serious TEAEs by Primary SOC and PT;
- 7. Summary of Serious TEAEs by Primary SOC, PT and maximum Severity;
- Summary of TEAEs Leading to Early Discontinuation of the Study Treatment by Primary SOC and PT.
- 9. Summary of TEAEs Leading to Temporary Interruption by Primary SOC and PT.
- 10. Summary of Most Frequent AEs (at least 2% in any treatment group) by PT

No inferential statistical tests will be applied to compare the treatment arms in terms of incidence of adverse events.

By-patient listings will be created for the following:

- 1. All Treatment Emergent Adverse Events
- 2. Serious Treatment Emergent Adverse Events
- 3. Treatment Emergent Adverse Events Leading to Treatment Discontinuation or Temporary Interruption
- 4. All Treatment Emergent Adverse Events in Patients with Fatal TEAEs

Adverse events occurred before the first administration of study treatment will only be listed.

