11.2.4 Screening Visit (V1, from Day -30 to Day -1)

The following procedures will be performed during the screening period:

- 1. Informed consent process and signature of the informed consent form (ICF). For subjects participating in the PK sub-study, the "PK-specific" consent signature should also be collected;
- 2. Demographics collection (age, sex, race) and health-related behaviour assessment (smoking habit, alcohol consumption, alcohol or drug abuse);
- 3. Relevant rosacea-associated medical history collection (including but not limited to family history for rosacea, age of onset etc.);
- 4. Relevant non-rosacea-associated medical history collection (attention will be paid to those medical conditions included in the exclusion criteria;
- 5. Record of previous and concomitant medications (attention will be paid to drug-associated exclusion criteria and prohibited treatments);
- 6. Vital signs recording (heart rate, blood pressure, body temperature);
- 7. Complete physical examination (including also measurement of height);
- 8. Rosacea-associated facial skin inflammatory lesion count (i.e. papules and pustules);
- 9. Five-points Investigator's Global Assessment (IGA) of Rosacea Severity;
- 10. Other rosacea-associated lesions assessment (i.e. facial erythema, facial telangiectasia, ocular manifestations, phymatous changes);
- 11. Visual analogue scale (VAS) for pain, burning/stinging and itching;
- 12. Blood collection and performance of the following laboratory tests (to be performed as close as possible to the randomisation visit [V2]):
 - haematological tests (haematocrit, haemoglobin, red blood cell count, white blood cell count with differential count, platelet count)
 - clinical chemistry tests (glycaemia, total cholesterol, triglycerides, serum creatinine, urea (or BUN), sodium, potassium, chloride, AST, ALT, Gamma-GT, alkaline phosphatase, total and fractioned bilirubin, erythrocyte sedimentation rate)
 - if not provided by the local laboratory, estimation of glomerular filtration rate
 - C-reactive protein
- 9. Urinalysis (specific gravity, pH, protein, glucose, ketones, haemoglobin, nitrite [if available], bilirubin, urobilinogen, and microscopic examination [if available]);
- 10. Serum pregnancy tests (women of child-bearing potential only);

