15. SAFETY ASPECTS

15.1 Adverse Events

15.1.1 Definition of Adverse Events

An adverse event (AE) is any untoward medical occurrence in a patient or clinical trial patient administered a medicinal product which does not necessarily have a causal relationship with this treatment. An adverse event can therefore be any unfavourable and unintended sign (including an abnormal laboratory finding), symptom, or disease temporally associated with the use of an investigational product, whether or not related to the investigational product.

An AE does include any:

- Exacerbation of pre-existing illness.
- Increase in frequency or intensity of a pre-existing episodic event or condition.
- Condition detected or diagnosed after study drug administration even though it may have been present prior to the start of the study.
- Continuous persistent disease or symptoms present at baseline that worsen following the start of the study.
- Symptoms associated with disease not previously reported by the patient.

An AE does not include a/an:

- Medical or surgical procedure (e.g., surgery, endoscopy, tooth extraction, transfusion); the condition that leads to the procedure is an AE.
- Planned medical or surgical procedures.
- Pre-existing diseases or conditions present or detected at the start of the study that do not worsen.
- Situations where an untoward medical occurrence has not occurred (e.g. hospitalization for cosmetic elective surgery, social and/or convenience admissions).
- The disease or disorder being studied, or sign or symptom associated with the disease or disorder unless more severe than expected for the patient condition.
- Overdose of other study drug or concurrent medication without signs or symptoms.
- Symptoms associated with the disease that are consistent with the patient usual clinical course unless the symptom(s) meet(s) the criteria for "serious" except for what detailed in chapter. 15.1.3.

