15.1.6 Documentation of Adverse Events

All AEs occurring during the study, after patient signature of the informed consent (with the exception described in chapters 15.1.1. and 15.1.3., events recorded in appropriate e-CRF pages), must be assessed and documented by the investigator on the AE pages of the subjects' e-CRF. If they meet the criteria for "serious" require also the completion of a SAE Report Form that must be immediately (within maximum 24 hours) reported to the Sponsor (section 15.1.7).

The Investigator will always provide his/her assessment of causality at the time of the initial report. Each AE will be assessed and documented by the investigator according to the following categories:

- Study protocol number.
- Study Centre number.
- · Patient identification number.
- Description of the sign and symptom/event.
- Severity as previously defined in Section 15.1.5.
- Duration: Record the onset and resolution time and dates of the event.
- Action taken.
- Causality to study treatment/individual component: as previously defined in section 15.1.5.
- Outcome
- Seriousness.

All AEs reported during the study must be followed-up by the Investigator until the event resolves, stabilises or the patient is lost to follow-up (see sec. 15.1.9.).

AEs still present at the end of the study period and for the subsequent 30 days must be followed until the final outcome is determined.

An AE that is initially reported as non-serious and later meets the criteria for a SAE, it must be reported as a SAE as soon as the information regarding the presence of one or more seriousness criteria become known to the Investigator.

The Investigator is responsible to ensure that the follow-up includes any supplemental investigations as may be indicated to elucidate as completely as practical, the nature and/or causality of the AE. This may include additional laboratory tests or investigations, histopathological examinations, or consultation with other health care professionals.

The Sponsor may request the Investigator to perform or arrange for the conduct of supplemental measurements and/or evaluations.

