15.1.9 Post study AEs and SAEs

Serious and non-serious AEs will be recorded, after patient signature of informed consent, from the Screening visit (V1) to the End of study visit (V5) or Early termination visit, regardless of whether the participant is on treatment.

SAEs will be recorded and reported as appropriate and followed-up until resolution or the patient is lost to follow up. Non-serious AEs will be recorded as appropriate and followed-up until End of Study

visit (V5, ESV) or Early Termination Visit (ETV) with event's outcome reporting.

SAEs will be recorded and reported as appropriate and followed-up until Resolution, Chronicity or the patient is lost to follow up.

SAEs still present at the end of the study period and for the subsequent 30 days, must be followed until a final outcome is determined or the patient is lost to follow up.

A post-study AE/SAE is defined as any event that occurs outside the AE/SAE detection period as defined previously.

Investigators are not obliged to actively seek AEs or SAEs after study termination. However, if the Investigator learns of any SAE, including death, at any time after a subject has been discharged from the study, and he/she considers the event reasonably related to the Investigational Product, the Investigator will promptly notify the Sponsor, according to the process explained at section 15.1.7.

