16.3.4 Statistical Analysis of Adverse Events

Adverse events will be presented for the Safety Analysis Set (SAF), by treatment group.
All adverse events will be assigned to a Preferred Term (PT) and will be classified by Primary SOC according to the latest MedDRA version.

Any adverse event which started at or after the first administration of study treatment will be considered as Treatment Emergent Adverse Event (TEAE). If the start date is missing for an AE, the AE will be considered to be treatment emergent.

Adverse events will be reported on a per-patient basis. This means that even if a patient reported the same event repeatedly, the event will be counted only once.

TEAEs relationship to study medications will be investigated with frequency tables. Missing classifications concerning study drug relationship will also be considered as treatment-related.

The following tables will be presented:

- 1. Overview of AEs and TEAEs showing the number of AEs and TEAEs and the number of patients with any AEs and TEAEs, treatment-related TEAEs, serious TEAEs, treatment-related serious TEAEs and TEAEs leading to study withdrawal;
- 2. Summary of TEAEs by Primary SOC and PT;
- 3. Summary of Related TEAEs by Primary SOC and PT;
- 4. Summary of TEAEs by Primary SOC, PT and maximum Severity;
- 5. Summary of Serious TEAEs by Primary SOC and PT;
- 6. Summary of Related and Serious TEAEs by Primary SOC and PT;
- 7. Summary of Serious TEAEs by Primary SOC, PT and maximum Severity;
- 8. Summary of TEAEs causing early discontinuation of the study treatment by Primary SO and PT.

No inferential statistical tests will be applied to compare the treatment arms in terms of incidence of adverse events.

Adverse events occurred before the first administration of study treatment will only be listed.

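### The treatment-emergent rule looks only at the start date, so an AE recorded in screening that becomes serious on drug can be missing from the TEAE and serious-TEAE tables

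*SAP*

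**What the plan says.** **The rule.** SAP 8.1: "Any adverse event which started at or after the first administration of study treatment will be considered as Treatment Emergent Adverse Event (TEAE". Protocol 16.3.4 has the same sentence. Neither has a clause for an event that started earlier and then worsened or became serious.

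**Earlier events.** Both sections say: "Adverse events occurred before the first administration of study treatment will only be listed". If the start date is unknown, the rule is: "If the start date is missing for an AE, the AE will be considered to be treatment emergent".

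**The outputs.** The serious-event tables in SAP 8.1 are restricted to treatment-emergent events, for example "Summary of Serious TEAEs by Primary SOC and PT". The related, severity and discontinuation tables have the same restriction, as do the by-patient listings of serious events and of events leading to discontinuation or interruption.

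**The collection period.** Protocol 15.1.9: "Serious and non-serious AEs will be recorded, after patient signature of informed consent, from the Screening visit (V1" visit onwards. The heading of Protocol 11.2.4 gives the window: "Screening Visit (V1, from Day -30 to Day -1".

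**Worsening and seriousness.** Protocol 15.1.1 counts as an AE: "Continuous persistent disease or symptoms present at baseline that worsen following the start of the study". Protocol 15.1.4 allows a worsening abnormal baseline laboratory value to be an AE. Protocol 15.1.6: "An AE that is initially reported as non-serious and later meets the criteria for a SAE, it must be reported as a SAE". That section asks for one onset and one resolution per AE, and for no date of worsening or of becoming serious. Protocol 15.1.5 makes the grades Severe, Life-threatening and Death seriousness criteria in themselves.

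**The concern.** Safety is a stated objective (Protocol 5, SAP 3.1), and its tabulated evidence consists almost wholly of TEAE tables. A start-date rule sorts each event by when it began and ignores what happened to it on drug. An event that was mild in screening and serious under treatment is important on-treatment information, yet it can be classed as pre-dose and left to a listing.

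The resulting error has one direction: it can only undercount on-treatment deterioration. Elsewhere SAP 8.1 resolves doubt the other way. A missing start date counts as treatment-emergent, a missing relationship as related, and a missing severity as severe.

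The setting makes the gap relevant. Protocol 8 and 15.2 name *Clostridium difficile* associated diarrhoea as a potential risk. Protocol 11.2.4 and 11.3 place a lactulose breath test (10 g) within the 14 days before randomisation. That gut symptoms would follow the test often is an inference; the documents give no rate.

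**Working it through.** No sample size, power or event count underlies this point, so the check is a reading of the TEAE rule against the recording rules.

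**Inputs**
- Start-only definition; pre-dose AEs listed only: SAP 8.1, Protocol 16.3.4.
- AE collection from screening: Protocol 11.2.4 and 15.1.9. Day -30 to Day -1 gives up to 30 pre-dose days.
- What counts as an AE: Protocol 15.1.1 and 15.1.4.
- Change to serious, and one onset per AE: Protocol 15.1.6.
- Severe is serious in itself: Protocol 15.1.5.
- Planned arm size of 67: Protocol 16.1, SAP 4.5.

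**Applying the rule case by case**
1. *A medical-history condition or baseline laboratory value that worsens on drug.* Protocol 15.1.1 and 15.1.4 allow the worsening to be an AE of its own. Its onset can be the date of worsening, so it is a TEAE. Not lost.
2. *An AE recorded in screening that worsens on drug without becoming serious.* If the site opens a new record at the worsening, it is a TEAE. If the site updates the old record, the start stays pre-dose and the event is only listed. Neither document says which to do.
3. *A non-serious AE recorded in screening that becomes serious on drug.* Protocol 15.1.6 has that AE reported as an SAE. With one onset per AE and no instruction to open a new record, the natural reading is that the pre-dose start stays. The event then fails the TEAE rule and is absent from the TEAE and serious-TEAE tables and from the serious-TEAE listing. It appears only among the listed pre-dose AEs.
4. *An AE with the start date wholly missing.* Counted as a TEAE.

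Case 3 is wider than hospitalisations. Because of Protocol 15.1.5, a screening AE that worsens to Severe on drug becomes serious and moves from case 2 to case 3.

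**Is there another table that would catch case 3?** The overview in Protocol 16.3.4 counts AEs alongside TEAEs. The overview in SAP 8.1 counts treatment-emergent events only, and SAP 10 does not list this change. SAP table 10 is labelled as AEs rather than TEAEs, but the listing-only sentence appears to keep pre-dose events out of it too.

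**Size per patient.** 1/67 = 0.0149, about 1.5 percentage points of an arm. Where the true count of patients with a serious event in an arm is 1, omitting that patient takes 1/67 (1.5%) to 0/67 (0%). The safety set is analysed by treatment actually received, so actual denominators may differ from 67.

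**The case against.** The strongest reply is that the recording rules already do the work. Protocol 15.1.1 treats exacerbations, increases in the intensity of episodic conditions and worsening baseline symptoms as AEs. Protocol 15.1.4 does much the same for laboratory values. Entered that way, a worsening has an on-treatment onset and is a TEAE. Protocol 15.1.6 can be read as a rule on when to report seriousness; it does not say that the old onset is kept or that a new record is barred. The convention may sit in the eCRF completion guidelines or user manual (Protocol 17.8, 17.10), which are not part of these documents.

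Much of this stands, and it rules out two stronger readings.
- A reader might infer that any on-drug worsening drops out of every TEAE table. The documents do not support that: case 1 is not lost, and case 2 is lost only under one recording habit. Nor would mild loose stools in screening followed by colitis on drug clearly be lost. Colitis could be entered as a condition newly diagnosed after dosing (15.1.1), and 15.1.7 prefers related SAEs to be reported together as a diagnosis.
- A reader might take the pre-dose share of collection time, at most 30 of 90 days, as the share of events affected. It is not an event rate. An affected event must start in screening, still be present at dosing, then worsen or become serious, and stay in the old record. The documents give no rate for any of these steps.

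It is also fair that other outputs keep part of the information. SAEs still reach the sponsor within 24 hours (Protocol 15.1.7). Reasons for discontinuation are tabulated by arm (Protocol 16.2.7, SAP 6.1). Chemistry and haematology have shift tables (SAP 8.3). Abdominal scores are compared as change from baseline (SAP 7.3.6).

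What the reply does not remove is that the stated definition has no worsening or seriousness clause, and that no instruction in either document makes sites record the change separately. Inclusion in the tables then depends on site habit across about 40 centres (Protocol 6).

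**Conclusion.** The point holds in a limited form. As written, and unless a site opens a new record, an AE recorded in screening that becomes serious on drug is left out of the TEAE and serious-TEAE tables and the TEAE listings. This includes one that worsens to Severe. For a screening AE that worsens but stays non-serious, the outcome turns on a convention the documents do not state.

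The conclusion assumes that the pre-dose onset is kept when an event is upgraded. That is the natural reading of Protocol 15.1.6 but not an explicit rule.

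How many events are affected cannot be derived from the documents. At the planned 67 per arm, each omitted patient is about 1.5 percentage points. The gap concerns the safety summaries; it does not touch expedited reporting or the efficacy analyses. It should be corrected, because the stated rule can err only towards too few on-treatment events and a better rule costs little.

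**What to change.** In SAP 8.1 and Protocol 16.3.4, define a TEAE as an AE that started at or after first dose, or that started earlier and increased in severity or became serious at or after first dose.

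State alongside it that such a change is entered as a new AE record, with its onset at the date of change and its own grade and seriousness. The two parts belong together: with a single onset per AE and no date of change, the wider definition cannot be programmed reliably.

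The cost is a sentence or two in each document and a note to sites on AE entry. No new assessment is needed, and SAP 2 already provides for amendments. The downside is that TEAE counts may be slightly higher.
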